### **9.2.1.2 Unanticipated Serious Adverse Device Effect**

#### **Unanticipated Serious Adverse Device Effect Definition**

An unanticipated serious ADE is a SADE effect that by its nature, incidence, severity, or outcome has not been identified in the current version of the risk analysis report.

### **9.2.2 Warnings and Precautions**

Unauthorized modification or repair of the control unit, its components, or supplies may result in unsafe conditions and/or impaired performance. No modification of this equipment is allowed without express authorization from ZELTIQ. Any unauthorized modification or repair will void the warranty.

CoolSculpting System use has not been studied in children, those who are pregnant or lactating, or who have:

- Known sensitivity to cold such as cold urticaria, Raynaud's disease, or Chilblains (pernio)
- Known sensitivity or allergy to fructose, glycerine, isopropyl alcohol, or propylene glycol
- Impaired peripheral circulation in the area to be treated
- Neuropathic disorders such as post-herpetic neuralgia or diabetic neuropathy
- Impaired skin sensation
- Open or infected wounds
- Bleeding disorders or concomitant use of blood thinners
- Recent surgery or scar tissue in the area to be treated
- Hernia in or adjacent to the treatment site
- Skin conditions such as eczema, dermatitis, or rashes in the area to be treated

### **9.2.3 Other Laboratory Variables**

Screening for pregnancy will be performed (urine  $\beta$ -HCG at Screening, Treatment 1, and at Treatment 2 only).

## **9.3 Data Safety Monitoring Board**

Not applicable.

### **9.3.1 Appropriateness of Measurements**

The efficacy and safety assessments planned for this study are widely used and generally recognized as reliable, accurate, and relevant to the disease condition.

## 10 STATISTICAL METHODS

The purpose of the study is to obtain PROs and have more subjects treated and studied at international sites. There is no statistical hypothesis to prove in this study. More details on the methods of statistical analysis, on statistical summary, and on the derivation of some statistical variables can be found from the statistical analysis plan.

### 10.1 Determination of Sample Size

The primary objective of this Phase IV study is to estimate the overall satisfaction rate, which is the proportion of subjects who report overall satisfaction with CoolSculpting treatment in real-world clinical settings. Consequently, the sample size will be based on providing reasonable precision for the estimate of overall satisfaction rate.

Previous studies conducted on subjects undergoing flank or abdominal fat reduction using CoolSculpting products reported moderately high overall satisfaction rate. The mean overall satisfaction rate was 65.8% from the study (protocol: ZA15-004) based on 19 subjects, and 63.3% from another study (Protocol: ZA10-001) based on 60 subjects. The weighted average of rates from the 2 studies, which is 63.9%, is now used as the initial estimate of the mean overall satisfaction rate for this planned study. A sample size of 98 subjects would provide a 10% margin of error (associated with 95% CI) for the estimate of the 63.9% expected rate. Allowing a 10% dropout during the study period, approximately 108 subjects will be needed for recruitment into the study.

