**Number of Subjects:**

Approximately 100 subjects will be enrolled at approximately 8 sites.

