## **Sample Size**

The sample size will be based on providing reasonable precision for the estimate of the overall satisfaction rate.

Previous studies conducted on subjects undergoing flank or abdominal fat reduction using CoolSculpting products reported moderately high overall satisfaction rate. The mean overall satisfaction rate was 65.8% from the study (Protocol: ZA15-004) based on 19 subjects, and 63.3% from another study (Protocol: ZA10-001) based on 60 subjects. The weighted average of rates from the 2 studies, which is 63.9%, is now used as the initial estimate of the mean overall satisfaction rate for this planned study. A sample size of 98 subjects would provide a 10% margin of error (associated with 95% CI) for the estimate of the 63.9% expected rate. Allowing a 10% dropout during the study period, approximately 108 subjects will be needed for recruitment into the study.

---

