## **7.3 Selection of Study Population**

### **7.3.1 Number of Planned Subjects**

Approximately 100 subjects will be enrolled at approximately 8 sites.

Refer to the statistical considerations on which the numbers are based in [Section 10.1](#).

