#### **7.3.4 Removal of Subjects from Therapy or Assessments**

Notification of early participant discontinuation from the study and the reason for discontinuation will be provided to the sponsor and will be clearly documented on the appropriate case report form (CRF).

Reasons for discontinuation from the study may include the following:

- Completed
- Other
- Physician decision
- Protocol deviation
- Screen failure
- Site terminated by sponsor
- Study terminated by sponsor
- Technical problems
- Withdrawal by subject
- Lost to follow-up

Subjects who do not comply with the protocol or who withdraw consent will not be replaced. Subjects who stop study treatment for any other reason will not be replaced. Subjects are free to withdraw from the study at any time without providing reason(s) for withdrawal and without prejudice to further treatment. The reason(s) for withdrawal will be documented in the CRF.

Subjects withdrawing from the study will be encouraged to complete the same final evaluations as subjects completing the study according to this protocol, particularly safety evaluations. The aim is to record data in the same way as for subjects who completed the study.

Reasonable efforts will be made to contact subjects who are lost to follow-up. These efforts must be documented in the subject's file.

The sponsor has the right to terminate the study at any time in case of SAEs or if special circumstances concerning the CoolSculpting procedure or the company occur, making further treatment of subjects impossible. In this event, the investigator(s) will be informed of the reason for study termination.

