#### **10.3.2.1 Primary Analyses**

The primary endpoint will be CSQ Item #1 measured at Week 12 for subjects who receive 1 treatment session and at Week 20 for subjects who receive 2 treatment sessions.

Subjects who have reported 'Very satisfied' and 'Satisfied' will be categorized as 'Satisfied.' The counts and percentage will be summarized and the 95% CI on the percentage will be calculated with normal approximation.

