10.2 PRIMARY ANALYSIS

The primary endpoint of the study will be the overall participant satisfaction based on CSQ Item question #1 at 12 weeks after the final treatment (measured at week 12 for participants who received 1 treatment session, week 20 for 2 treatment sessions) for non-invasive fat reduction in CoolSculpting participants, including participants who receive treatment in the abdomen alone, flanks alone, or both abdomen and flanks.

The CSQ consists of 3 versions: CSQ-Abdomen, CSQ-Flank, CSQ-Abdomen and Flank; Participants with abdomen only treatment will be administered only the CSQ-Abdomen. Participants with flank only treatment will be administered only the CSQ-Flank version. Participants with both abdomen and flank treatments will be administered all 3 versions (CSQ-Abdomen, CSQ-Flank, and CSQ-Abdomen and Flank)); however, only CSQ-Abdomen and Flank will be used for the primary analysis. In each version, the CSQ Item question #1 is “Rate your overall satisfaction with the fat reduction procedure on the treated area”, with the following categories:

- Very satisfied
- Satisfied
- Neither satisfied nor dissatisfied
- Dissatisfied
- Very dissatisfied

‘Very satisfied’ and ‘Satisfied’ will be categorized as a new category, ‘Satisfied’.

The number and percentage of participants will be presented by category at 12 weeks after the final treatment, regardless of the CSQ version.

Furthermore, the 95% confidence interval on the proportion by category at 12 weeks after the final treatment, regardless of the CSQ version will be calculated using normal approximation method.

10.3 **SECONDARY ANALYSES**

All secondary endpoints will be measured at Week 12 for participants who received 1 treatment session and at Week 20 for participants who received 2 treatment sessions. The following analyses will be provided:

- Proportion of participants by treated area(s) (abdomen, flanks, and both abdomen and flanks) with “satisfied” or “very satisfied” on the CSQ Item #1.
- Proportion of participants by number of treatment cycles who received 1 or 2 treatment sessions with “satisfied” or “very satisfied” on CSQ Item #1.
- Proportion of participants with “Satisfied” or “Very Satisfied” on CSQ Item #1 by BMI categories (18.5 - < 25, 25 - ≤ 30)
- Mean change in volume of fat from baseline as measured by 3D photography.

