The count and percentage of participants with the same categories as the primary endpoint for CSQ Item #1 will be summarized and the 95% CIs for the percentages will be calculated.

Descriptive summary statistics of change in volume of fat from baseline will be provided by visit.

[REDACTED]

[REDACTED]

[REDACTED]

[REDACTED]

[REDACTED]

[REDACTED]

[REDACTED]

[REDACTED]

[REDACTED]

- █ [REDACTED]
- █ [REDACTED]
- █ [REDACTED]
- █ [REDACTED]
- █ [REDACTED]

[REDACTED]

[REDACTED]

[REDACTED]

[REDACTED]

[REDACTED]

11.1 **SAFETY ANALYSES**

The safety analyses will be based on the safety population.

11.2 **ADVERSE EVENTS**

Adverse events (AEs) will be collected throughout the study beginning with the first treatment visit. Adverse events will be coded by system organ class and preferred term using the *Medical Dictionary for Regulatory Activities*, version 22.0 or newer. AEs, AE severity, and causality are defined in the protocol (Section 11.1).

An AE will be considered a treatment-emergent (TEAE) if the AE began or worsened (increased in severity or became serious) on or after the treatment start date and time. An AE is considered an ADE if the AE with a reasonable possibility (Possible, Probable, or Causal relationship) that the device caused the event. An AE is considered a study procedure related AE if the AE with a reasonable possibility (Possible, Probable, or Causal relationship) that the procedure caused the event.

Overall summary of TEAEs, SAEs, ADEs, SADEs, study procedure related AEs, TEAEs leading to study discontinuation, and deaths will be presented as total and by treatment session. AEs/ADEs occurred on or after the date of treatment sessions 1 and before the date of treatment session 2 are counted for treatment session 1; AEs/ADEs occurred on or after the date of treatment sessions 2 are counted for treatment sessions 2.

The number and percentage of participants will be summarized by System Organ Class (SOC) and Preferred Term (PT), with or without by severity, as total and by treatment session as follows:

- TEAEs by SOC and PT
- TEAEs by SOC, PT, and severity
- ADEs by SOC and PT
- ADEs by SOC, PT, and severity
- Study Procedure Related AE by SOC and PT
- Treatment-emergent Serious AEs (SAEs) by SOC and PT
- Serious ADEs (SADEs) by SOC and PT
- TEAEs leading to study discontinuation by SOC and PT

The AE summary tables by SOC and PT will be presented with SOC in alphabetical order and in decreasing frequency within each SOC.

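### The enrolment target is about 100 in two places and about 108 in three, and the SAP's normal-approximation interval, if applied to each CSQ Item #1 response, breaks down for rare or empty responses (both minor)

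*Protocol*

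**What the plan says.** **Target.** The protocol synopsis, under Number of Subjects, says "Approximately 100 subjects will be enrolled at approximately 8 sites". Protocol 7.3.1 repeats the figure and adds "Refer to the statistical considerations on which the numbers are based in" Section 10.1. Section 10.1, the synopsis Sample Size text and SAP 15.0 give different numbers. They start from an expected satisfaction rate of 63.9%, state "A sample size of 98 subjects would provide a 10% margin of error (associated with 95% CI" for that rate, and finish with "Allowing a 10% dropout during the study period, approximately 108 subjects will be needed for recruitment into the study" (the SAP writes participants for subjects). Protocol 7.3.4 says "Subjects who do not comply with the protocol or who withdraw consent will not be replaced", and the same holds for subjects who stop treatment for other reasons. Protocol 10.2 defines the enrolled population as everyone who signs consent. Screen failure is a listed discontinuation reason in Protocol 7.3.4 and SAP 7.1.

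**Interval.** Protocol 10.3.2.1 combines the two favourable responses into one satisfied category and says "the 95% CI on the percentage will be calculated with normal approximation". SAP 10.2 lists all five responses, adds the combined category, asks for number and percentage by category, and then plans "the 95% confidence interval on the proportion by category at 12 weeks after the final treatment", again by normal approximation. SAP 10.3 says "The count and percentage of participants with the same categories as the primary endpoint for CSQ Item #1 will be summarized", with 95% intervals, but names no method. SAP 12.1 asks for subgroup analyses, including each site and country, and mentions no interval. SAP 18.0 declares no change from the protocol.

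**The concern.** A precision-based study has one sample-size claim, and here it carries two recruitment figures. The cross-reference in 7.3.1 rules out treating them as independent roundings: the section it points to does not yield its number. A site or ethics committee working from 7.3.1 would stop at about 100, while the statistical text promises 98 evaluable after dropout.

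On the interval, the normal approximation suits a proportion near 64% with 90 or more subjects. It does not suit a response that hardly anyone chooses, such as very dissatisfied may be. A table could then print a negative percentage as a lower limit, or a zero-width interval that claims more certainty than 90 subjects can give.

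**Working it through.** **1. The plan's own figures**

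- Weighted rate: (19 × 65.8% + 60 × 63.3%) / 79 = 63.9%. This agrees with the plan.
- Dropout: 98 × 1.1 = 107.8, so 108, as stated. Division gives 98 / 0.9 = 108.9, so 109. The difference is trivial.
- Size for 10 points by the plain normal approximation: 1.96² × 0.639 × 0.361 / 0.10² = 88.6, so 89. This does not give 98.
- With a continuity correction, the half-width is 1.96 × √(0.639 × 0.361 / n) + 1/(2n). At n = 98 it is 10.02 points, close to the stated margin; 99 subjects bring it under 10. An exact (Clopper-Pearson) half-width needs 96. Since 89 × 1.1 = 97.9 also rounds to 98, a second dropout allowance cannot be ruled out. The documents name no formula.

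**2. What each target delivers**

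- 100 × 0.9 = 90 evaluable, 8 below the stated 98.
- 108 × 0.9 = 97.2, so about 97.

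| Evaluable n | Half-width, plain (points) | Half-width, continuity-corrected (points) |
|---|---|---|
| 90 | 9.92 | 10.48 |
| 97 | 9.56 | 10.07 |
| 98 | 9.51 | 10.02 |

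These counts assume that the 10% loss is the only loss. If the target counts people who sign consent, screen failures reduce the evaluable number further.

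**3. Interval for a single response**

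The interval is p ± 1.96 × √(p(1 − p)/n), with p = x/n.

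- x = 0: p = 0, so the limits are 0% and 0% at any n. For 0/90, Wilson gives 0% to 4.1%.
- The lower limit is negative when 0 < x < n × 1.96² / (n + 1.96²). The bound is 3.68 at n = 90 and 3.70 at n = 98, so this affects x = 1, 2 or 3.
- Example, 1/90: −1.1% to 3.3%. Wilson gives 0.2% to 6.0%.

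How often this occurs depends on the true response rates, which the plan does not give. At n = 90:

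| Assumed true rate | Chance of no responses | Chance of 3 or fewer (including none) |
|---|---|---|
| 1% | 0.99^90 = 40% | 99% |
| 3% | 0.97^90 = 6% | 72% |
| 5% | 0.95^90 = 1% | 34% |

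Coverage by exact binomial enumeration, averaged over evenly spaced true rates:

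| True rates | n | Normal approximation | Wilson |
|---|---|---|---|
| 1% to 5% | 90 | 85% | 96% |
| 1% to 5% | 98 | 86% | 96% |
| 5% to 20% | 90 and 98 | 93% | 95% |
| 55% to 75% (overall satisfied) | 90 and 98 | 94.4% | 95% |

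The loss is confined to rare responses. The overall satisfied rate is barely affected.

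**The case against.** **Target.** Every figure is qualified as approximate, the study tests no hypothesis, and the 10-point margin holds at n = 90 by the interval the plan will use. Neither target delivers exactly 98. All of this stands and makes the matter editorial. It does not remove the conflict, because 7.3.1 rests its 100 on a section that gives 108.

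A reader might go further and infer that 100 enrolled fails the precision goal. The documents do not support that. It is true only under a continuity-corrected formula, which the plan never names; the analysis interval is described only as a normal approximation.

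**Interval.** By category in SAP 10.2 could mean the combined category alone. The declaration of no change in SAP 18.0 favours that reading, since the protocol's interval is for the combined percentage. The five-response list, and the preceding sentence asking for counts by category, favour the wider one. I find the wider reading the natural one, but it is not certain.

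A second tempting inference concerns the site tables. Take 8 equal sites with 11 or 12 evaluable subjects each, and split the 36.1% not satisfied evenly over three responses, about 12% each. Coverage would be 75% to 78%, and about 5 to 6 of 24 site-by-response cells would be empty (24 × 0.88^11 = 5.9; 24 × 0.88^12 = 5.2). These numbers are illustrative only. They also need a normal-approximation interval to be shown for each response at each site, and SAP 12.1 mentions no interval. The table specifications are in a separate document. What stands is that the method is unstated in SAP 10.3, and in 12.1 for any interval shown there.

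**Conclusion.** Both parts hold and both are minor. Neither threatens the primary result.

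- **Target:** the contradiction is textual and needs no assumption. At the plan's 10% dropout without replacement, 100 gives about 90 evaluable where 98 are stated. The cost in precision is about 0.4 points of half-width (9.92 against 9.51). Whether 10 points is met depends on the unstated formula: yes by the plain normal approximation, no (10.48) with a continuity correction.
- **Interval:** on the natural reading of SAP 10.2, the failure for 0 to 3 responses is algebraic and certain when such counts occur. How often they occur, and the 85% to 86% coverage, rest on assumed true rates of 1% to 5%. On the narrow reading, the full-sample problem disappears, but the SAP should say so. The overall satisfied interval is sound at 94.4% average coverage.

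**What to change.** **Target.** Put one figure in all five places: the synopsis (Number of Subjects and Sample Size), Protocol 7.3.1, Protocol 10.1 and SAP 15.0. Give with it the evaluable number, the half-width and the formula. Under the plain normal approximation, the choices are about 100, giving about 90 evaluable and 9.9 points, or about 108, giving about 97 evaluable and 9.6 points. Say whether the target counts subjects who consent, which is the plan's meaning of enrolled, or subjects treated. If it counts consents, allow for screen failures as well as dropout.

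**Interval.** In SAP 10.2, either use the Wilson interval for the single responses or state that the interval is for combined satisfied only. Name Wilson as the method in SAP 10.3, and in 12.1 wherever an interval is shown. Keep the pre-specified normal approximation for the overall satisfied rate.

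**Cost.** Wording in five places for the target and three SAP sections for the interval, plus one software option. Keeping 100 lowers the stated evaluable number from 98 to about 90. It needs no extra subjects if the target counts treated subjects and there are no screen failures; otherwise more must consent. Keeping 108 means about 8 more than 7.3.1 states. Two interval methods would then appear in the CSQ Item #1 tables, so footnote each; a supplementary Wilson interval for the overall rate would make the tables comparable.

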### 10.2 Populations for Analyses

For purposes of analysis, the following populations are defined:

Population	Description
Enrolled	All participants who sign informed consent
Evaluable	All participants who sign the ICF, have at least one of the procedures conducted, and also report the CSQ Item #1 at 12 weeks after the final treatment (measured at Week 12 for participants who receive 1 treatment session and at Week 20 for participants who receive 2 treatment sessions).
Safety	All participants who have at least one of the procedures conducted.

### 10.3 Statistical Analyses

The statistical analysis plan will be developed and finalized before database lock and will describe the participant populations to be included in the analyses. This section is a summary of the planned statistical analyses of the primary, secondary endpoints, exploratory endpoints, and safety parameters.

#### 10.3.1 Disposition, Baseline and Study Information

In general, the disposition data, patient baseline and characteristics data, and concomitant therapy data will be summarized descriptively. The categorical variables will be presented with

count and percentage and the continuous variables will be presented with mean, standard deviation, median, minimum, and maximum.

#### **10.3.1.1 Patient Disposition**

The number of subjects who have enrolled into the study, the number and percentage of subjects who have had the procedure, and the number and percentage of subjects who have had all follow-up visits will be summarized.

The number and percentage of subjects who are evaluable and the number of subjects who are in safety population will be also summarized.

#### **10.3.1.2 Patient Baseline and Characteristics**

Demographics (age, sex, and race) of subjects will be summarized.

A summary on height, weight, and BMI will be also provided. The number and percentage of subjects by BMI category (18.5 to < 25; 25 to ≤ 30) will also be provided.

#### **10.3.1.3 Concomitant Therapy**

Concomitant therapy that a patient has during the study will be recorded and summarized.

#### **10.3.1.4 Treatment Compliance**

Treatment compliance will not be applicable in the study.

### **10.3.2 Efficacy Analyses**

The evaluable patient population will be the analysis population used for efficacy.

#### **10.3.2.1 Primary Analyses**

The primary endpoint will be CSQ Item #1 measured at Week 12 for subjects who receive 1 treatment session and at Week 20 for subjects who receive 2 treatment sessions.

Subjects who have reported 'Very satisfied' and 'Satisfied' will be categorized as 'Satisfied.' The counts and percentage will be summarized and the 95% CI on the percentage will be calculated with normal approximation.

#### **10.3.2.2 Secondary Analyses**

All secondary endpoints will be measured at Week 12 for subjects who receive 1 treatment session and at Week 20 for subjects who receive 2 treatment sessions. The analyses on the secondary endpoints will include:

- Proportion of subjects by treated area(s) (abdomen alone, flanks alone, and both abdomen and flanks) with "satisfied" or "very satisfied" on CSQ Item #1.

### **10.3.3 Safety Analyses**

The safety population will be the analysis population used for safety analyses.

Frequency of AEs including SAEs and ADEs including SADEs will be summarized.

